## **7. ASSESSMENTS**

Every effort should be made to ensure that the protocol-required tests and procedures are completed as described. However, it is anticipated that from time to time there may be circumstances, outside of the control of the investigator, that may make it unfeasible to perform the test. In these cases the investigator will take all steps necessary to ensure the safety and well-being of the patient. When a protocol-required test cannot be performed, the investigator will document the reason for this and any corrective and preventive actions that he or she has taken to ensure that normal processes are adhered to as soon as possible. The study team will be informed of these incidents in a timely fashion.

### **7.1. Safety Assessment**

Safety assessments will include collection of AEs, serious adverse events (SAEs), vital signs and physical examination, electrocardiogram (ECG) [12-lead], laboratory assessments, including pregnancy tests and verification of concomitant treatments.

#### **7.1.1. Pregnancy Testing**

For female patients of childbearing potential, a serum or urine pregnancy test, with sensitivity of at least 25 mIU/mL and assayed in a certified laboratory, will be performed on 2 occasions prior to starting study treatment – once at the start of screening and once at Cycle 1 Day 1 immediately before investigational product administration. Following a negative pregnancy result at screening, appropriate contraception must be commenced and a

further negative pregnancy result will then be required at the Cycle 1 Day 1 visit: within 5 days after the first day of the menstrual period counting the first day as Day 1 > before the patient may receive the investigational product. Pregnancy tests will also be routinely repeated at every cycle during the active treatment period, at the end of study treatment, and additionally whenever 1 menstrual cycle is missed or when potential pregnancy is otherwise suspected. In the case of a positive human chorionic gonadotropin (hCG) test, the patient will be withdrawn from treatment and from the study. Additional pregnancy tests may also be undertaken if requested by institutional review board (IRB)/ ethics committees (ECs) or if required by local regulations.

### **7.1.2. Adverse Events**

Assessment of AEs will include the type, incidence, severity (graded by the NCI CTCAE version 4.03) timing, seriousness, and relatedness. Patients must be followed for AEs for 28 days after the last study treatment administration or until all drug-related toxicities have resolved, whichever is later; or earlier than 28 days should the patient commence another anti-cancer therapy in the meantime.

Adverse events that occur during the study, will be recorded on the AE CRF page.

### **7.1.3. Laboratory Safety Assessment**

Haematology, blood chemistry, coagulation and urinalysis will be drawn at the time points described in the [Schedule of Activities](#) and analyzed at local laboratories. Cycle 1 Day 1 hematology, blood chemistry, coagulation and urinalysis assessments do not need to be repeated if the screening assessment is performed within 7 days prior to that date. Assessments collected on dosing days should be obtained within 48 hours prior to dosing.

**Table 4. Laboratory Assessments**

| Hematology           | Chemistry                | Coagulation | Urinalysis  | Pregnancy Test  | Unique Screening Labs   |
|----------------------|--------------------------|-------------|---|---|---|
| Hemoglobin           | ALT                      | PT or INR   | Urine dipstick for urine protein:
If positive collect 24-hr and microscopic (Reflex Testing) | For female patients of childbearing potential, serum or urine (to be specified in the protocol) | Hepatitis B surface antigen
Hepatitis B core antibody
Hepatitis C antibody
HIV |
| Platelets            | AST                      | PTT         |   |   |   |
| WBC                  | Alk Phos                 |             | Urine dipstick for urine blood:
If positive collect a microscopic (Reflex Testing)           |   | FSH – for post-menopausal women   |
| Absolute Neutrophils | Sodium                   |             |   |   |   |
| Absolute Lymphocytes | Potassium                |             |   |   |   |
| Absolute Monocytes   | Magnesium                |             |   |   |   |
| Absolute Eosinophils | Chloride                 |             |   |   |   |
| Absolute Basophils   | Total Calcium            |             |   |   |   |
|                      | Total Bilirubin***       |             |   |   |   |
|                      | BUN or Urea              |             |   |   |   |
|                      | Creatinine               |             |   |   |   |
|                      | Uric Acid                |             |   |   |   |
|                      | Glucose (non-fasted)     |             |   |   |   |
|                      | Albumin                  |             |   |   |   |
|                      | Phosphorous or Phosphate |             |   |   |   |

\*\*\* For potential Hy's Law cases, in addition to repeating AST and ALT, laboratory tests should include albumin, creatine kinase, total bilirubin, direct and indirect bilirubin, gamma-glutamyl transferase, prothrombin time (PT)/INR, and alkaline phosphatase.

**7.1.4. Vital Signs and Physical Examination**

Patients will have a physical examination (PE) to include weight, vital signs, assessment of Karnofsky performance status and height; height will be measured at screening only.

A complete PE will be performed at Screening, Cycle 1 Day 1 and at the End of Treatment visit for each patient and will include an assessment of all body systems (including neurological examination, genitourinary examination is optional). The Cycle 1 Day 1 assessment does not need to be repeated if the screening assessment is performed within 7 days of dosing. Findings of all physical examinations should be recorded in the source documents, and any change from baseline considered by the investigator to be clinically significant should be recorded as an AE in the CRF.

Abbreviated PEs should be performed as appropriate per the Schedule of Activities, and on an as needed basis for assessment of AEs. Abbreviated exams should include a neurological exam as well as be targeted to specific symptoms or complaints and be consistent with local standard of care.

Vital signs will include measurements of blood pressure and temperature (oral, tympanic, temporal or axillary). On dosing days, vital signs should be measured prior to administration of any of the study treatments. Sitting blood pressure (BP) will be measured with the patient's arm supported at the level of the heart and recorded to the nearest mmHg. The same arm (preferably the dominant arm) should preferably be used throughout the trial. A BP cuff, which has been properly sized and calibrated, should be used to measure BP. The use of automated devices for measuring BP is acceptable.

#### **7.1.5. (12-Lead) Electrocardiogram**

Electrocardiogram (ECG): Triplicate 12-lead (with a 10-second rhythm strip) tracing will be used for all ECGs, except the screening assessment. It is preferable that the machine used has a capacity to calculate the standard intervals automatically. At each time point (see the [Schedule of Activities](#)), 3 consecutive ECGs will be performed at approximately 2 minutes apart to determine the mean QTcF interval. If the mean QTcF is prolonged ( $>500$  msec, ie, CTCAE Grade  $\geq 3$ ), then the ECGs should be re-evaluated by a qualified person at the site for confirmation as soon as the finding is made, including verification that the machine reading is accurate. If manual reading verifies a QTcF of  $>500$  msec, immediate correction for reversible causes (including electrolyte abnormalities, hypoxia and concomitant medications for drugs with the potential to prolong the QTcF interval) should be performed. In addition, repeat ECGs should be immediately performed hourly for at least 3 hours until the QTcF interval falls below 500 msec. If QTcF interval reverts to less than 500 msec, and in the judgment of the investigator(s) and sponsor is determined to be due to cause(s) other than investigational product, treatment may be continued with regular ECG monitoring. If in that timeframe the QTcF intervals rise above 500 msec the investigational product will be held until the QTcF interval decreases to 500 msec. Patients will then restart the investigational product at the next lowest dose level. If the QTcF interval has still not decreased to  $<500$  msec after 2-weeks, or if at any time a patient has a QTcF interval  $>515$  msec or becomes symptomatic, the patient will be removed from the study. Additional triplicate ECGs may be performed as clinically indicated.

Prior to concluding that an episode of prolongation of the QTcF interval is due to investigational product, thorough consideration should be given to potential precipitating factors (eg, change in patient clinical condition, effect of concurrent medication, electrolyte disturbance) and possible evaluation by specialist.

If patient experiences a cardiac or neurologic AE (specifically syncope, dizziness, seizures, or stroke), an ECG (triplicate) should be obtained at the time of the event.

When matched with PK sampling, the ECG must be carried out before each PK sample drawing such that the PK sample is collected at the nominal time (ie, the timing of the PK collections over rides the timing of the ECG collections).

CCI [Redacted]

CCI [Redacted]

CCI [Redacted]

CCI [Redacted]

[Redacted]

[Redacted]

[Redacted]

CCI [Redacted]

CCI [Redacted]

CCI [Redacted]

CCI [REDACTED]

CCI [REDACTED]

CCI [REDACTED]

### 7.3. Biomarker and Pharmacodynamic Assessments

One of the key elements of this study is the possibility to evaluate potential molecular targets that could be modified in vivo by PF-06840003 used in this study. The biomarker studies will be used to help understand the in vivo mechanism of action of the agent(s) studied as well as potential mechanisms of resistance. The studies may help in the future development of this drug as a single agent, or in combination with other compounds.

Table 5 summarizes representative assays to be used and the source of the samples. Refer to the Schedule of Activities for details pertaining to specific days of sample collection and to the study manual for details of sample preparation.

**Table 5. Pharmacodynamic Summary**

| Assay  | Source                       |
|---|-------------------------------------|
| Measurement of kynurenine, tryptophan, and metabolites by mass spectrometry | Peripheral blood, Tumor Tissue, CSF |
| CCI [REDACTED]  | CCI [REDACTED]                      |
| Assessment of serum cytokines and chemokines                                | Peripheral Blood Serum              |
| CCI [REDACTED]  | CCI [REDACTED]                      |
| mRNA profiling (Part 2 only)  | Tumor Tissue                        |
| TCR sequencing (Part 2 only)  | Tumor Tissue                        |

#### 7.3.1. Target Engagement – Assessment of Kynurenine, Tryptophan and Metabolites

Blood samples (approximately 4 mL of whole blood) will be collected for the evaluation of pharmacodynamic markers; kyn, trp, and metabolites for patients as outlined in the [Schedule of Activities](#). Details regarding the collection, processing, storage and shipping of these samples will be provided in the study manual.

The levels of kyn, trp, and metabolites in whole blood samples will be determined using a qualified analytical method in compliance with Pfizer standard operating procedures.

An assay specific for the detection of kyn, trp, and metabolites will be developed. This assay will provide proof of mechanism (target engagement) as IDO1 is a protein that catalyzes the first step in trp catabolism to N-formyl-kynurenine, and trp degradation by IDO1 yields a series of kynurenes.

CCI [REDACTED]

CCI [REDACTED]

CCI [REDACTED]

CCI [REDACTED]

[REDACTED]

### 7.3.3. Cytokines and Chemokines

Blood samples (approximately 4 mL) to provide approximately 1 mL serum for analysis of serum cytokine and chemokines will be collected at times specified in the [SOA](#).

Instructions for sample collection, processing, storage and shipment will be provided in the laboratory manual.

Samples collected for this purpose will be retained in accordance with local regulations and if not used within this timeframe, will be destroyed.

### 7.3.4. T Cell Receptor (TCR) Sequencing

Whole blood samples (approximately 10 mL) for evaluation of T cell receptor usage, clonality, and frequency will be collected at the times specified in the [SOA](#).

Instructions for sample collection, processing, storage and shipment will be provided in the laboratory manual.

### **7.3.5. Tumor Biopsies**

Patients enrolled into the trial must have access to their archival formalin-fixed paraffin embedded material containing tumor that is of diagnostic quality and representative of their diagnosed malignancy. A fresh pre-treatment biopsy is acceptable if archival tumor is not available. If required, the screening biopsy should preferably be obtained after all eligibility criteria have been verified. Tissue blocks are preferred, but freshly-cut paraffin sections are acceptable and must comprise 10-15 paraffin sections, 4-microns in thickness, cut within 1 week of submission, and placed individually on unstained, unbaked charged glass microscope slides.

Additionally, fresh pre-treatment and on-treatment biopsies are optional. On-treatment biopsy samples are to be collected on Cycle 2 Day 1 and should preferably be taken from the same lesion and from a lesion that has not been previously irradiated. Biopsies collected within 30 days of registration will be acceptable.

Biomarker evaluation will be performed on the biopsies. Analyses will be conducted at an IHC reference lab and include IHC assessment of IDO1 in addition to lymphocyte markers such as CD4, CD8, CD3 and exploratory biomarkers. RNA profiling will be conducted to explore immune-modulatory (immune effector and tolerance-associated) and checkpoint, cytokine, chemokine transcripts, IO and non-IO gene signatures in Part 2 only. Additionally, evaluation of TCR usage, clonality, and frequency via TCR sequencing may be performed.

Instructions for sample collection, processing, storage and shipment will be provided in the study manual. Samples may be retained in accordance with local regulations and if not used within this timeframe, will be destroyed.

### **7.4. Tumor Response Assessments**

Tumor assessments will include all known or suspected disease sites. A standard contrast-enhanced cranial MRI will be performed at screening/baseline and every 8 weeks ( $\pm 5$  days). Non-contrast cranial MRI may only be used to document disease in those patients who are allergic to contrast. Tumor assessments should be repeated at the end of treatment visit if more than 4 weeks have passed since the last evaluation.

The same imaging technique used to characterize each identified and reported lesion at screening will be employed in the following tumor assessments.

Anti-tumor activity will be assessed through radiological tumor assessments conducted at screening, during treatment as specified in the Schedule of Activity, whenever disease progression is suspected (eg, symptomatic deterioration), and at the time of withdrawal from treatment (if not done in the previous 4 weeks). All patients' files and radiologic images must be available for source verification and for potential peer review.

Assessment of response will be made using the Macdonald criteria, RANO and iRANO. Disease progression will be confirmed with two consecutive timepoints at least 8 weeks apart in the absence of substantial neurological decline if progressive disease is suspected within 6 months of treatment initiation. Responses should be confirmed with two assessments at

least 4 weeks apart. Efficacy evaluations using the Macdonald criteria involve post-contrast MRI findings, non-contrast T1 and T2 fluid attenuated inversion recovery (FLAIR) images, use of corticosteroid dose, and neurological examination as defined below:

**Complete Response (CR) – ALL of the following:**

- Complete disappearance of all enhancing measurable and non-measurable disease sustained for  $\geq 4$  weeks.
- No new lesions.
- Stable or improved non-enhancing (T2/FLAIR) lesions.
- Off-steroids.
- Neurological condition stable or improved.

**Partial Response (PR) – ALL of the following:**

- Greater than or equal to 50% decrease compared to baseline in the sum of the perpendicular diameters of all measurable enhancing lesions sustained for at least 4 weeks.
- No progression of non-measurable disease.
- No new lesions.
- Stable or improved non-enhancing (T2/FLAIR) lesions on the same or lower dose of corticosteroids compared with baseline scan.
- The corticosteroid dose at the time of the scan evaluation should be no greater than the dose at the time of the baseline scan.
- Neurological condition stable or improved.

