**Progressive Disease (PD) – ANY of the following:**

- Greater than or equal to 25% increase in the sum of the products of perpendicular diameters of enhancing lesions compared to the smallest tumor measurement obtained either at baseline (if no decrease) or best response, on stable or increasing dose of corticosteroids\*.
- Significant increase in T2/FLAIR non-enhancing lesion on stable or increasing dose of corticosteroids compared with baseline scan or best response following initiation of therapy\*, not due to co-morbid events (eg, radiation therapy, demyelination, ischemic injury, infection, seizures, post-operative changes, or other treatment effects).

- Any new lesion.
- Clinical deterioration not attributable to other causes apart from the tumor (eg, seizures, medication side effects, complications of therapy, cerebrovascular events, infection, etc.) or changes in corticosteroid dose.
- Failure to return for evaluation due to death or deteriorating condition.
- Clear progression of non-measurable disease.

\*Stable doses of corticosteroids includes patients not on corticosteroids.

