**Stable Disease (SD):**

- Does not qualify for CR, PR, or PD.
- Stable non-enhancing (T2/FLAIR) lesions on same or lower dose of corticosteroids compared with baseline scan. In the event that the corticosteroid dose has been increased, the last scan considered to show SD will be the scan obtained when the corticosteroid dose was equivalent to the baseline dose.
- Stable clinically.

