**Table 6. Overall Response Criteria**

|                         | CR   | PR   | SD    | PD |
|-------------------------|-------------|-------------|--------------|-----------------------|
| T1-Gd                   | None        | ≥50%↓       | <25%↑- <50%↓ | ≥25%↑*                |
| T2/FLAIR                | Stable or ↓ | Stable or ↓ | Stable or ↓  | ↑*                    |
| New Lesion              | None        | None        | None         | Present*              |
| Corticosteroids         | None        | Stable or ↓ | Stable or ↓  | NA                    |
| Clinical Status         | Stable or ↑ | Stable or ↑ | Stable or ↑  | ↓*                    |
| Requirement of response | All         | All         | All          | Any*                  |

1. Progression occurs when any of the criteria with \* are present; NA: increase in corticosteroid dose alone will not be taken into account in determining progression in the absence of persistent clinical deterioration

CR=complete response; PR=partial response; SD=stable disease; PD=progressive disease; ↓=decrease; ↑=increase

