8.2.5.1. Primary Efficacy Analysis

Tumor assessments including MRI will be performed every 8 weeks (with an allowable window per study protocol) after the first dose. Disease control rate (DCR), defined as the proportion of patients achieving CR, PR, or SD as assessed by Macdonald criteria, will be summarized and listed by dose level and week. A cycle is 4 weeks long. Number of weeks will be derived based on cycle numbers. This will be performed for Part 1 and Part 2 separately. If deemed necessary and data permits, a combined analysis may be performed where Part 2 and the same dose level in Part 1 as that in Part 2 will be combined. These analyses will be based on investigator provided overall disease assessment.

As data accumulates, a Bayesian approach with a non-informative Jeffery's prior beta (0.5, 0.5) will be used to calculate the posterior probability of observing certain DCR (eg, 40%, 50%, 60% etc.). The purpose of it is to monitor data on an ongoing basis and to provide more analytical data for the study team. No official analysis output needs to be generated for this. This is only applicable to Part 2.

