8.2.5.2. Secondary Efficacy Analysis

ORR with Macdonald Criteria

Objective tumor response (ORR), defined as the proportion of patients achieving CR or PR as assessed by Macdonald criteria, will be summarized and listed by dose level week. This will be performed for Part 1 and Part 2 separately. If deemed necessary and data permits, a combined analysis may be performed where Part 2 and the same dose level in Part 1 as that in Part 2 will be combined.

As data accumulates, a Bayesian approach with a non-informative Jeffery's prior beta (0.5, 0.5) will be used to calculate the posterior probability of observing certain ORR (eg, 5%, 10%, 15%, or 20% etc.). The purpose of it is to monitor data on an ongoing basis and to provide more analytical data for the study team. No official analysis output needs to be generated for this. This is only applicable to Part 2.

For example, if 2 responders were observed in the first 10 patients enrolled, the posterior probability of observing 20% ORR is about 53.3%; if 2 responders were observed in the first 12 patients enrolled, the posterior probability of observing 20% ORR is about 41.5%; if only 1 responder was observed in the first 15 patients enrolled, the posterior probability of observing 20% ORR is about 8.7%. If a posterior probability is less than 15% for both of the 2 efficacy endpoints, the study team may choose to stop the expansion phase for futility. The safety data will also be reviewed in that decision-making process.

DCR with RANO Criteria

Overall DCR based on Response Assessment for Neuro-Oncology (RANO) criteria will be summarized by week. The analysis will be based on investigator provided overall response in the Response Assessment in Neuro-Oncology. This will be performed for Part 1 and Part 2 separately. If deemed necessary and data permits, a combined analysis may be performed where Part 2 and the same dose level in Part 1 as that in Part 2 will be combined.

CCI

On the basis of RANO,

the key component of iRANO is specific additional guidance for the determination of PD among neuro-oncology patients undergoing immunotherapy. Specifically, iRANO advocates the confirmation of radiographic progression in appropriate patients defined by clinical status and time from initiation of immunotherapy. Other details related to the PD confirmation will be documented in the Programming Plan.

PFS

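### Partial response is written on the sum of diameters but progression on the sum of products, so Macdonald ORR could be misclassified if sites apply the text literally

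*Protocol*

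**What the plan says.** Protocol section 7.4 introduces its response definitions as the ones to be used for the Macdonald assessment.

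- **PR:** a reduction of 50% or more, worded as a "decrease compared to baseline in the sum of the perpendicular diameters of all measurable enhancing lesions". The reduction has to last 4 weeks or longer, and there are further conditions on new lesions, T2/FLAIR, corticosteroids and neurological status.
- **PD:** "Greater than or equal to 25% increase in the sum of the products of perpendicular diameters of enhancing lesions" relative to the smallest measurement, or any of several other events.
- **SD:** the residual class, "Does not qualify for CR, PR, or PD", with stable T2/FLAIR lesions and a stable clinical state.
- **Table 6:** one T1-Gd row holds all three size cut-offs: a fall of 50% or more for PR, a rise of 25% or more for PD, and SD for everything between. The row does not name the quantity measured.

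The SAP builds its endpoints on these categories. ORR is "defined as the proportion of patients achieving CR or PR as assessed by Macdonald criteria" (section 8.2.5.2) and DCR is "defined as the proportion of patients achieving CR, PR, or SD as assessed by Macdonald criteria" (section 8.2.5.1). Neither section gives a size formula. The DCR section uses the investigator's overall assessment.

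Macdonald objective response is a secondary endpoint. Even so, protocol section 9.3 and SAP section 4.3 say that the Part 2 sample size is driven by Week 9 DCR and ORR by MRI. ORR is also one of the two endpoints in the discretionary futility rule.

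**The concern.** The PR sentence measures a length and the PD sentence measures an area. The single T1-Gd row in Table 6 is coherent only if PR, SD and PD share one measure, so the text and the table cannot both be followed as they stand. Both sentences are intact in the current protocol, and nothing in the SAP settles the matter.

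These are the only written size rules that investigators have. If one site follows the PR wording and another uses products, identical scans receive different categories. A patient whose lesion area falls by half can be a responder at one site and stable at the other. What is at stake is the ORR count, and with it the ORR power claim, the ORR half of the futility rule and any duration-of-response summary.

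**Working it through.** **1. The plan's own power figures.** Inputs from protocol section 9.3: n = 20, one-sided alpha 0.05, ORR 5% against 20%, DCR 40% against 65%. The formula is the normal approximation with null variance in the critical value and alternative variance in the power:

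power = Φ{ [p1 − p0 − 1.645·√(p0(1−p0)/n)] / √(p1(1−p1)/n) }

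- ORR: (0.15 − 1.645 × 0.0487) / 0.0894 = 0.781, so power is 78.3% (stated: about 78%).
- DCR: (0.25 − 1.645 × 0.1095) / 0.1067 = 0.655, so power is 74.4% (stated: about 75%).

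Both stated figures are reproduced.

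**2. One lesion shrinking in proportion.** If each diameter is multiplied by s, the sum of diameters scales with s and the product with s².

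- Written rule, s = 0.5: area falls by 1 − 0.5² = 75%.
- Product rule, s² = 0.5: each diameter falls by 1 − √0.5 = 29.3%. Under the written rule this patient is SD.

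**3. One elongated lesion, neither axis growing.** The smallest area loss that satisfies the written rule is:

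| Axis ratio | Smallest qualifying area loss |
|---|---|
| 1:1 | 75.0% |
| 2:1 | 71.9% |
| 3:1 | 66.7% |
| 4:1 | 62.5% |

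For 4:1 the diameters sum to 5 and must fall to 2.5. The most area is kept with axes 1.5 and 1, which leaves 1.5 of 4.

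**4. Several lesions.** Take one 4×4 lesion unchanged and two 2×2 lesions gone. The sum of diameters goes from 8 + 4 + 4 = 16 to 8, a fall of 50%, so the written size rule is met. The sum of products goes from 16 + 4 + 4 = 24 to 16, a fall of 33%, so a product rule is not met. Here the written rule is the looser one.

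**5. Illustration for ORR.** Assume that ORR is 20% on the product scale, that a share f of those responders misses PR under the written rule, and that the 5% null is unchanged. The documents do not give f.

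| f | ORR as scored | Power (formula in step 1) |
|---|---|---|
| 0 | 20% | 78.3% |
| 10% | 18% | 71.9% |
| 25% | 15% | 59.8% |
| 50% | 10% | 32.6% |

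**6. DCR and futility.** A patient who misses PR only on the size rule normally becomes SD and still counts in DCR. The futility rule needs a posterior probability below 15% for both endpoints, so only its ORR half can move. That half is sensitive. With the plan's Beta(0.5, 0.5) prior, 2 responders in 15 give Beta(2.5, 13.5) and a probability of 27.4% that ORR exceeds 20%. One responder in 15 gives 8.7%, which matches the protocol's own example. Reclassifying one patient can therefore take the ORR half across the 15% line, but the rule is met only if DCR has also fallen below it.

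**The case against.** The best reply is that the PR wording is probably a dropped phrase. Sites are told to use the Macdonald criteria, Table 6 implies a single scale, and response categories appear to be assigned by investigators rather than programmed from diameters. Sites may already be using products, in which case ORR is unaffected. That is plausible, and it is why the effect has to be stated conditionally. It does not remove the contradiction, because the written PR rule still says something different and nothing tells a site to depart from it.

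A reader might go further in three ways that the documents do not support.

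- **That PR always demands a 75% area reduction.** This holds only for proportional shrinkage. Steps 3 and 4 show smaller requirements and one case where the direction reverses.
- **That ORR is understated by a known and large amount, so that an active drug would look inactive.** A log-normal model of area change, with equal shrinkage in both directions and 20% product-scale responders, leaves only 1.3% to 6.2% meeting the written rule for a log SD of 0.5 to 1.0. The same formula gives about 9.6% and 11.7% for a log SD of 1.5 and 2.0. Neither the model nor its spread comes from the documents. It also allows no complete disappearance, although complete responses count in ORR and the PR wording does not touch them. The documents do not say on which scale the 5% and 20% rates were set.
- **That the futility threshold would be met too easily.** The rule needs both endpoints below 15%, DCR is essentially unmoved, and stopping is at the team's discretion.

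**Conclusion.** The inconsistency is real and unresolved: PR and PD are written on different measures, and neither Table 6 nor the SAP settles which applies. If sites apply the PR text literally, Macdonald ORR can be misclassified, most likely downwards, because lesions that shrink roughly in proportion face a 75% area threshold instead of 50%.

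The size cannot be derived from the documents. The illustrative fall in power from about 78% to about 72%, 60% or 33% rests on an assumed product-scale ORR of 20%, an unchanged 5% null, and an assumed 10%, 25% or 50% of responders missing PR. The Part 2 primary efficacy endpoint, DCR, is essentially unaffected, and futility is touched only through its ORR half. The correction should be made because ORR helps to set the sample size, but the point does not undermine the primary efficacy analysis.

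**What to change.** In the PR definition of protocol section 7.4, replace the sum of perpendicular diameters with the sum of the products of perpendicular diameters, as in the PD definition. Name that measure in the T1-Gd row of Table 6. Send sites a short note so that all assessments use one rule. It would also help to repeat the measure in SAP section 8.2.5.2 and to state that the 5% and 20% ORR rates are on that scale, if that was the intent.

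The cost is a few words in an amendment and a site communication. Both rules use the same perpendicular diameters, so no new data are needed. If any PR or SD assessments have already been recorded, the sponsor should ask which rule the site used and re-score them from the recorded diameters where it was the sum.
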